6.2.3 Clinical Laboratory Determinations

Blood and urine samples for clinical laboratory tests will be collected at the visits outlined in Table 1. Hematology, chemistry, and urinalysis will be conducted at these visits. The investigator will assess the clinical significance of any values outside the reference ranges provided by the central laboratory. A central laboratory will be used to evaluate all urine and blood samples, which will be collected, processed, and stored according to the instructions provided by the laboratory. Patients with abnormalities judged to be clinically significant at Screening (Visit 1) will be excluded from the study. WOCBP will be required to have a urine pregnancy test at all visits. A positive pregnancy test at Visit 1 or Visit 2 will exclude the patient from participation in the study. Investigators may also perform unscheduled clinical laboratory determinations at any time for the purpose of patient safety. Patients are not required to fast overnight before coming in for their appointments.

The clinical laboratory parameters to be measured are shown in Table 3.

Table 3 Clinical Laboratory Parameters

Category	Parameter
Chemistry	Sodium, potassium, chloride, bicarbonate, glucose, blood urea nitrogen, creatinine, total bilirubin, alkaline phosphatase, aspartate aminotransferase, alanine aminotransferase, lactate dehydrogenase, creatine kinase, total protein, albumin, calcium, phosphorus, uric acid, total cholesterol, high density lipoprotein, low density lipoprotein, total triglycerides; the estimated glomerular filtration rate will be calculated by the central laboratory
Hematology	Hemoglobin; hematocrit; red blood cell count; red blood cell indices (mean corpuscular volume, mean corpuscular hemoglobin, mean corpuscular hemoglobin concentration); white blood cell count, including differential (neutrophils, lymphocytes, monocytes, eosinophils, and basophils); platelet count
Urinalysis	Urine dipstick for specific gravity, pH, protein, glucose, ketones, bilirubin, and blood; microscopic examination including red blood cells/high-power field, white blood cells/high-power field, and casts/low-power field

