5.1.1.4.3 Clinical Laboratory Assessments

Clinical laboratory assessments will be summarized by treatment group for the Safety Population as follows:

Table 5-21 Clinical Laboratory Summaries

Endpoint	Description	Timing	Methodology
Number and percentage of participants with Potentially Clinically Significant (PCS) values ¹	Summary by laboratory category, parameter, and PCS criteria 
 Parameters and PCS criteria specified in Section 6.3.5.1 N1 (percentage denominator) = Participants with non-missing non-PCS baseline and ≥ 1 postbaseline parameter assessment 	Randomization to End of Study ³	PCS descriptives
Descriptives ²	Summary by laboratory category and parameter in SI units and in conventional units and analysis visit 
 Parameters specified in Section 6.3.5.3 	Randomization to End of Study ³	CFB descriptives
Shift from baseline	Summary by laboratory parameter and category 
 Low, normal, and high categories provided by central laboratory Parameters specified in Section 6.3.5.3 	End of Study ³	Shift analysis
Liver function findings ⁴	Summary of number and percentage by hepatic laboratory parameter and PCS categories. Definition of PCS categories see Table 6-10 in Section 6.3.4.2.	Randomization to End of Study ³	Categorical descriptives
Adjudication results of ALT or AST elevations ⁵	Summary of relationship of ALT or AST elevation to study medication for participants with adjudicated case (i.e., ALT $\geq 3 \times$ ULN and/or AST $\geq 3 \times$ ULN) by the following categories: 
 Probable Possible Unlikely Insufficient data Summary will be provided for the incidence by number of participants and by number of events	Randomization date to End of Study ³	Categorical descriptives

ALT = aspartate aminotransferase; AST = aspartate aminotransferase; TBL = total bilirubin; ALP = alkaline phosphatase; INR = international normalized ratio; ULN = upper limit of normal.

¹ Participants who report ≥ 1 postbaseline PCS value will have their laboratory visits with PCS values and all AEs listed.

² Clinical laboratory results and comments will be listed.

³ Analysis visits defined in Section 6.2.2.

Endpoint	Description	Timing	Methodology
----------	-------------	--------	-------------

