6.3.5 Clinical Laboratory Assessments

6.3.5.1 Potentially Clinically Significant Criteria

Laboratory assessments values meeting *any* of the following PCS low or PCS high criteria will be categorized as PCS:

Table 6-12 Clinical Laboratory PCS Criteria

Laboratory Group	Parameter	SI Unit	PCS Low Limit	PCS High Limit
Hematology	Basophils, absolute cell count	$10^9/L$	—	$> 2.0 \times ULN$
	Eosinophils absolute cell count	$10^9/L$	—	$> 2 \times ULN$
	Hematocrit	Ratio	$< 0.9 \times LLN$	$> 1.1 \times ULN$
	Hemoglobin	g/L	$< 0.9 \times LLN$	$> 1.1 \times ULN$
	Lymphocytes absolute cell count	$10^9/L$	$< 0.7 \times LLN$	$> 1.3 \times ULN$
	Monocytes, absolute cell count	$10^9/L$	$< 0.5 \times LLN$	$> 2.0 \times ULN$
	Neutrophils absolute cell count	$10^9/L$	$< 0.7 \times LLN$	$> 1.3 \times ULN$
	Platelet count (thrombocytes)	$10^9/L$	$< 0.5 \times LLN$	$> 1.5 \times ULN$
	Red blood cell count	$10^{12}/L$	$< 0.9 \times LLN$	$> 1.1 \times ULN$
	White blood cell count	$10^9/L$	$< 0.9 \times LLN$	$> 1.5 \times ULN$
Chemistry	Alanine aminotransferase	U/L	—	$> 3 \times ULN$
	Albumin	g/L	$< 0.8 \times LLN$	$> 1.2 \times ULN$

Laboratory Group	Parameter	SI Unit	PCS Low Limit	PCS High Limit
	Alkaline phosphatase	U/L	—	> 3 × ULN
	Aspartate aminotransferase	U/L	—	> 3 × ULN
	Bicarbonate	mmol/L	< 0.9 × LLN	> 1.1 × ULN
	Bilirubin, total	μmol/L	—	> 1.5 × ULN
	Blood urea nitrogen	mmol/L	—	> 1.5 × ULN
	Calcium	mmol/L	< 0.9 × LLN	> 1.1 × ULN
	Chloride	mmol/L	< 0.9 × LLN	> 1.1 × ULN
	Cholesterol, total	mmol/L	—	> 1.6 × ULN
	Creatinine	μmol/L	—	> 1.5 × ULN
	Creatine kinase	U/L	—	> 2.0 × ULN
	Glucose, nonfasting	mmol/L	< 0.8 × LLN	> 2 × ULN
	Lactate dehydrogenase (LDH)	U/L	—	> 3.0 × ULN
	Phosphorus	mmol/L	< 0.9 × LLN	> 1.1 × ULN
	Potassium	mmol/L	< 0.9 × LLN	> 1.1 × ULN
	Protein, total	g/L	< 0.9 × LLN	> 1.1 × ULN
	Sodium	mmol/L	< 0.9 × LLN	> 1.1 × ULN
	Triglycerides	mmol/L	—	> 2.0 × ULN
	Uric acid (urate)	μmol/L	—	> 1.2 × ULN
Urinalysis	Glucose	mmol/L	—	Positive
	pH	pH	< 0.9 × LLN	> 1.1 × ULN
	Protein	g/L	—	Positive
	Specific gravity	—	—	> 1.1 × ULN

LLN = lower limit of normal (value provided by the laboratory); PCS = potentially clinically significant; SI = *Le Système International d'Unités* (International System of Units); ULN = upper limit of normal (value provided by the laboratory).

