6.3.5.3 Continuous Descriptives and Shift Table Parameters

The following laboratory parameters will be summarized:

Table 6-14 Clinical Descriptive and Shift Table Parameters

Category	Parameters
Chemistry	Sodium, potassium, chloride, bicarbonate, glucose, blood urea nitrogen, creatinine, total bilirubin, alkaline phosphatase, aspartate aminotransferase, alanine aminotransferase, lactate dehydrogenase, creatine kinase, total protein, albumin, calcium, phosphorus, uric acid, total cholesterol, high density lipoprotein, low density lipoprotein, total triglycerides
Hematology	Hemoglobin; hematocrit; red blood cell count; red blood cell indices (mean corpuscular volume, mean corpuscular hemoglobin, mean corpuscular hemoglobin concentration); white blood cell count, including differential (neutrophils, lymphocytes, monocytes, eosinophils, and basophils); platelet count
Urinalysis	Specific gravity, pH

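### The only PCS limit for urine specific gravity, 1.1 × ULN, cannot fall below 1.100, so if true urine values stay under 1.10 the row shows 0% in every arm

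*SAP*

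**What the plan says.** Protocol section 7.3.2.3 leaves the laboratory PCS criteria to the SAP, so SAP Table 6-12 is the operative rule. Under section 6.3.5.1, laboratory values meeting any "of the following PCS low or PCS high criteria will be categorized as PCS".

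In the urinalysis block of that table, the row for "Specific gravity" has a dash for the unit, a dash for the low limit, and a high limit of more than 1.1 × ULN. The footnote says where the reference limit comes from: "ULN = upper limit of normal (value provided by the laboratory". No numeric ULN is given. Protocol section 6.2.3 (Table 3) gives the method of measurement: "Urine dipstick for specific gravity, pH, protein, glucose, ketones, bilirubin, and blood".

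The criterion feeds SAP Table 5-21, which reports the number and percentage of participants with PCS values by treatment group: "Summary by laboratory category, parameter, and PCS criteria". Footnote 1 of that table uses a postbaseline PCS value as the trigger for listing the participant's PCS laboratory visits and adverse events.

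Specific gravity is also reported elsewhere. Table 6-14 names "Specific gravity, pH" as the urinalysis parameters for the descriptive and shift tables. The shift uses "Low, normal, and high categories provided by central laboratory", with no multiplier, and is timed at End of Study.

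**The concern.** A multiplier on the ULN works for a quantity measured from zero, such as an enzyme activity or a cell count. Specific gravity is measured from 1.000, the value for water, and its information lies in the second and third decimals above that. Raising the upper limit by 10% adds about 0.10 to a quantity whose normal excess over water is a few hundredths. The limit therefore lands far from the laboratory's own limit, and the row has no low criterion as an alternative route to a flag.

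What is at stake is how a by-arm safety row is read. If the limit cannot be met, the 0% comes from the rule and not from the patients, and the row cannot separate the arms. The PCS row also has a role that the shift table does not fill. Under SAP section 6.2.2 every postbaseline assessment counts towards PCS, whereas the shift looks only at End of Study. A transient high value could be counted by a working PCS row and missed by the shift.

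**Working it through.** The plan states no absolute limit, so there is no figure to reproduce. The check is direct arithmetic on the stated rule.

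**Inputs**
- Multiplier 1.1, high side only (SAP Table 6-12).
- ULN = U, supplied by the laboratory and not in the documents. Assumed here to be 1.020 to 1.040, with 1.015 and 1.050 as wider bounds.
- Value for water: 1.000, by the definition of specific gravity.

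**Step 1: lowest possible limit.** Limit L = 1.1 × U. An upper limit for urine cannot be below water, so U ≥ 1.000 and L ≥ 1.1 × 1.000 = 1.100. This holds whatever ULN the laboratory uses.

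**Step 2: limit for assumed ULNs, and its distance from water relative to the ULN's own distance, (L − 1)/(U − 1).**

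| Assumed U | L = 1.1 × U | (L − 1)/(U − 1) |
|---|---|---|
| 1.015 | 1.1165 | 0.1165/0.015 = 7.8 |
| 1.020 | 1.1220 | 0.1220/0.020 = 6.1 |
| 1.025 | 1.1275 | 0.1275/0.025 = 5.1 |
| 1.030 | 1.1330 | 0.1330/0.030 = 4.4 |
| 1.035 | 1.1385 | 0.1385/0.035 = 4.0 |
| 1.040 | 1.1440 | 0.1440/0.040 = 3.6 |
| 1.050 | 1.1550 | 0.1550/0.050 = 3.1 |

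The flag therefore needs an excess over water of roughly three to eight times the excess at the laboratory's upper limit.

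**Step 3: invert the rule.** The ULN needed for a given limit is U = L/1.1. A limit of 1.035 needs U = 1.035/1.1 = 0.941, and a limit of 1.050 needs U = 1.050/1.1 = 0.955. Both are below water and cannot be upper limits for urine.

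**Step 4: consequence for the table.** Assume genuine urine values, and the dipstick scale, stay below 1.10. Then no true postbaseline value exceeds L and the numerator is 0 in each arm. The denominator (SAP Table 5-2, method M3, and Table 5-21) is participants with a non-missing, non-PCS baseline and at least one postbaseline value. Every arm reports 0%.

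**The case against.** The strongest reply is that little depends on this row. Specific gravity remains in the by-visit descriptives, which include the maximum, in the End of Study shift against the laboratory's own limits, and in the full laboratory listings. Protocol section 6.2.3 also has the investigator assess any value outside the reference range. No study objective, event of clinical interest or adverse-event category of interest depends on it. All of that stands, and it limits the point to one descriptive row.

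A second reply is that the decisive premise is external: neither document gives an attainable range for urine. That is also correct, so the premise is stated as an assumption. It leaves a wide margin. Even a ULN of 1.050 lies only half as far above water (0.050) as the lowest possible limit (0.100).

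Three stronger readings are tempting, and the documents do not support them.
- A reader might infer that the row must be zero whatever is recorded. A recording or unit error, such as 1030 entered for 1.030, could still produce a flag. The statement concerns true values.
- A reader might report the result as 0 of 400 per arm. The 400 is the planned number randomized. The ubrogepant Safety population requires at least one dose, and the PCS denominator requires a non-PCS baseline and a postbaseline value.
- A reader might extend the point to urine pH, which takes 0.9 × LLN and 1.1 × ULN on a logarithmic scale. With an assumed LLN of 4.5 to 5.0 and ULN of 8.0 to 9.0, the limits are 4.05 to 4.5 and 8.8 to 9.9. These are wide, but nothing shows that they cannot be reached.

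**Conclusion.** The point holds for the single specific gravity cell. The limit is at least 1.100 for any possible ULN, and 1.122 to 1.144 for assumed ULNs of 1.020 to 1.040. Assuming true values stay below 1.10, following the plan exactly gives an uninformative 0% of evaluable participants in each arm. A specific gravity result can then never bring a participant into the listing of PCS visits with adverse events.

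This is a badly scaled threshold. No stated figure is miscalculated and no two passages conflict. It does not leave specific gravity unreported, and the trial's safety conclusion does not turn on it. It is a minor correction, worth making because a 0% in a by-arm PCS table can be taken for a finding.

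**What to change.** In SAP Table 6-12, do one of the following:
- Replace the specific gravity high limit with the central laboratory's high flag (> ULN). The row then covers every postbaseline assessment, which the End of Study shift does not. The cost is some non-specific flags, for example from dehydration, and a looser criterion than the table's other numeric rows, all of which use a multiplier. The table already departs from multipliers where they do not fit: urine glucose and protein are flagged on a positive result.
- Delete the row and rely on the low/normal/high shift. This loses nothing that the row could have shown, but leaves no categorical summary of specific gravity before End of Study.

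Either way the change is to one row, with matching edits to the table and listing specifications and no new data. The urine pH criteria need no change on this account.

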6.3.5.2 Hepatic Laboratory Abnormalities

The selected event is of clinical interest: Elevated ALT or AST lab value that is ≥ 3 times the ULN. The following laboratory parameters will be summarized:

Table 6-13 Criteria for Hepatic Laboratory Abnormalities

Laboratory Parameter	Categories
ALT	>= 1 × ULN
	>= 1.5 × ULN
	>= 2 × ULN
	>= 3 × ULN
	>= 5 × ULN
	>= 10 × ULN
	>= 20 × ULN
AST	>= 1 × ULN
	>= 1.5 × ULN
	>= 2 × ULN
	>= 3 × ULN
	>= 5 × ULN
	>= 10 × ULN
	>= 20 × ULN
ALT or AST	>= 1 × ULN
	>= 1.5 × ULN
	>= 2 × ULN
	>= 3 × ULN
	>= 5 × ULN
	>= 10 × ULN
	>= 20 × ULN
Bilirubin Total	>= 1 × ULN
	>= 1.5 × ULN
	>= 2 × ULN
	>= 3 × ULN
	>= 5 × ULN
	>= 10 × ULN
	>= 20 × ULN
Alkaline Phosphatase	>= 1 × ULN
	>= 1.5 × ULN
	>= 2 × ULN
	>= 3 × ULN
	>= 5 × ULN

Laboratory Parameter	Categories
	$\geq 10 \times \text{ULN}$
	$\geq 20 \times \text{ULN}$
Concurrent Elevations ¹	ALT or AST $\geq 3 \times \text{ULN}$ AND Bilirubin Total $\geq 1.5 \times \text{ULN}$
	ALT or AST $\geq 3 \times \text{ULN}$ AND Bilirubin Total $\geq 2 \times \text{ULN}$
Potential Hy's Law ¹	ALT or AST $\geq 3 \times \text{ULN}$ AND Bilirubin Total $\geq 2 \times \text{ULN}$ AND ALP $< 2 \times \text{ULN}$

LLN = lower limit of normal (value provided by the laboratory); PCS = potentially clinically significant; SI = Le Système International d'Unités (International System of Units); ULN = upper limit of normal (value provided by the laboratory).

¹ Elevations are from the same day

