6.2.2 Events of Clinical Interest

Selected nonserious and serious events are of clinical interest and will require immediate reporting, recording and follow-up. The following events will be closely monitored:

- Suicidal ideations with intent, with or without a plan, (ie, Type 4 or 5 on the C-SSRS) or any suicidal behaviors
- Elevated ALT or AST laboratory value that is ≥ 3 times the ULN
- Potential Hy's law cases: elevated ALT or AST laboratory value that is ≥ 3 times the ULN and an elevated total bilirubin laboratory value that is ≥ 2 times the ULN and, at the same time, an alkaline phosphatase laboratory value that is < 2 times the ULN.

Reporting requirements for ALT or AST elevations and potential Hy's law cases are outlined in Sections 9.5 and 9.6. Responses to the C-SSRS that meet the above criterion will be captured in the electronic tablet (eTablet) and monitored by Allergan. Events that are determined to be AEs or SAEs must be reported appropriately via the designated eCRF pages and forms.

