7.3.2.7 Potential Hy's Law

Potential Hy's Law criteria within a 24-hour window is defined by a postbaseline elevation of alanine aminotransferase (ALT) or aspartate aminotransferase (AST) ≥ 3 times the ULN, along with total bilirubin (TBL) ≥ 2 times the ULN and a nonelevated alkaline phosphatase (ALP) < 2 times the ULN, all based on blood draws collected within a 24-hour period.

Potential Hy's Law criteria without time window (evaluation of drug-induced serious hepatotoxicity [eDISH]) is defined by maximum of postbaseline elevation of ALT or AST ≥ 3 times the ULN, along with maximum of postbaseline elevation of TBL ≥ 2 times the ULN.

Patients who meet the potential Hy's Law criteria from randomization to Visit 16 will be summarized. Supportive tabular displays also will be provided.

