⁴ Details of all participants with any liver function laboratory findings will be listed. For participants who met ALT $\geq 3 \times \text{ULN}$ or AST $\geq 3 \times \text{ULN}$, their ALT, AST, TBL, ALP, and INR assessments, and all AEs will be listed for all study visits. In addition, if available, their abnormal liver biochemistries risk factors, liver disease signs and symptoms, liver diagnostic tests, specialist consultation, liver lab tests, and drug screen will also be listed.

⁵ Participants with at least one adjudicated case (i.e. ALT $\geq 3 \times \text{ULN}$ or AST $\geq 3 \times \text{ULN}$) will be listed with their ALT and AST assessments, adjudication dates, adjudication results and confounding factors for all study visits.

Evaluation of drug-induced serious hepatotoxicity (eDISH) plot (scatter plot of maximum total bilirubin vs. maximum ALT) will be generated. The ALT, AST, total bilirubin, and ALP values over time will be overlaid on the same plot along with indicators for dosing times for each participant with ALT or AST elevation ($\geq 3 \times \text{ULN}$).

5.1.1.4.3.1 Potential Hy's Law

Potential Hy's Law criteria will be summarized by treatment group for the Safety Population as follows:

Table 5-22 Potential Hy's Law Summaries

Endpoint	Description	Timing	Methodology
Potential Hy's Law within 24-hour window	Number and percentage of participants with postbaseline assessment of the following laboratory parameters based on blood draws collected within a 24-hour period: 
 ALT or AST $\geq 3 \times \text{ULN}$ TBL $\geq 2 \times \text{ULN}$ ALP $< 2 \times \text{ULN}$ 	Randomization to End of Study ¹	Categorical descriptives
Potential Hy's Law without window (e-DISH)	Number and percentage of participants with postbaseline assessment of the following laboratory parameters at any time: 
 Maximum ALT or AST $\geq 3 \times \text{ULN}$ Maximum TBL $\geq 2 \times \text{ULN}$ 	Randomization to End of Study ¹	Categorical descriptives

e-DISH = evaluation of drug-induced serious hepatotoxicity.

ALT = alanine aminotransferase; AST = aspartate aminotransferase; TBL = total bilirubin.

ALP = alkaline phosphatase; ULN = upper limit of normal.

¹ Analysis visits defined in Section 6.2.2.

Participants who meet the Potential Hy's Law criteria will have their ALT, AST, TBL, and ALP assessment listed for all study visits.

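### SAP Table 6-13 counts potential Hy's law by same day, while SAP Table 5-22 and the protocol use 24 hours, so one report can carry two counts under one label

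*SAP*

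**What the plan says.** Two SAP tables carry a potential Hy's law category with identical limits: ALT or AST at least 3 x ULN, total bilirubin at least 2 x ULN, ALP below 2 x ULN.

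- **SAP 6.3.5.2, Table 6-13.** Footnote 1 is attached to the potential Hy's law row and to both concurrent-elevation rows (ALT or AST at least 3 x ULN with bilirubin at least 1.5 or at least 2 x ULN). It reads "Elevations are from the same day".
- **SAP 5.1.1.4.3.1, Table 5-22, first row.** "Number and percentage of participants with postbaseline assessment of the following laboratory parameters based on blood draws collected within a 24-hour period".
- **SAP Table 5-22, second row (e-DISH).** "Number and percentage of participants with postbaseline assessment of the following laboratory parameters at any time". This row uses maxima and has no ALP condition.
- **Protocol 7.3.2.7.** The windowed definition is "all based on blood draws collected within a 24-hour period".
- **SAP Table 5-21, liver function findings.** "Summary of number and percentage by hepatic laboratory parameter and PCS categories". For the category definitions it sends the reader to Table 6-10 in Section 6.3.4.2. That table describes how adverse event categories are built. The hepatic laboratory categories are in Table 6-13, Section 6.3.5.2.

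The protocol's reporting text gives no window in hours. Section 6.2.2 says only "at the same time, an alkaline phosphatase laboratory value that is" below 2 x ULN, and Section 9.6 lists the three limits without any timing. No text reconciles the same-day rule with the 24-hour rule, and SAP 5.2 reports no change to the planned analyses from the protocol.

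**The concern.** Table 5-21 and Table 5-22 both produce numbers and percentages of participants by treatment group. If the timing rules differ, the two outputs can give different potential Hy's law counts for the same arm, with nothing in the label to tell the reader why. Hepatic findings get close attention here: Protocol Section 1 says that ALT increases stopped two earlier compounds of this class, Protocol 3.1 sets up an adjudication committee, and Protocol 9.6 treats each potential Hy's law case as a serious adverse event. With counts expected near zero, a difference of one case would be visible and would have to be explained.

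**Working it through.** The plan states no figure on this point, so there is none to reproduce. The check is whether the two rules can classify the same patient differently, and in which direction.

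**Inputs.** The limits and timing rules come from SAP Tables 6-13 and 5-22 and Protocol 7.3.2.7. The four analytes sit in one chemistry panel (Protocol 6.2.3, Table 3: "total bilirubin, alkaline phosphatase, aspartate aminotransferase, alanine aminotransferase"). The repeat after ALT or AST at least 3 x ULN is due at 48 to 72 hours (Protocol 9.5). Unscheduled laboratory tests are allowed (Protocol 6.2.3 and 8.6). Planned size is 400 per arm (Protocol 4.1).

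**Step 1: constructed draw patterns.** Values are multiples of ULN. ALP is 1 x ULN wherever it is measured. The 16:00 and 09:00 draws are 8 + 9 = 17 hours apart.

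| Pattern | Same-day rule | 24-hour rule |
|---|---|---|
| A. One panel meets all criteria | yes | yes |
| B. 16:00: ALT 4, bilirubin 1.8; 09:00 next day: ALT 2.8, bilirubin 2.1 | no | yes |
| C. As B, but ALT still 4 next morning | yes | yes |
| D. ALT only on day 1; bilirubin and ALP only at 09:00 next day | no | yes |
| E. As B, but second draw at 48 hours | no | no |
| F. Values as B, both draws on one date (08:00 and 20:00) | yes | yes |

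Only B and D are discordant. In both, the components fall on consecutive dates and the second draw does not qualify alone.

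**Step 2: direction.** Two draws on one date are less than 24 hours apart, so every same-day case is a 24-hour case. A grid of first-draw times and gaps up to 24 hours, in 10-minute steps, gives 144 x 144 = 20,736 pairs. Of these, 10,296 meet both rules, 10,440 meet only the 24-hour rule and 0 meet only the same-day rule. The Table 6-13 count can therefore equal the Table 5-22 count or fall below it, never exceed it. The grid share, 10,440/20,736 = 50.3%, assumes uniform draw times and gaps. It is illustrative and does not predict how often discordance would occur.

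**Step 3: size.** Summaries are by treatment group, so one discordant case is 1/400 = 0.25% of an arm at planned size, or 1/800 = 0.125% of the two ubrogepant arms together.

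**Step 4: which rows have a wider counterpart.** The potential Hy's law row has the 24-hour row of Table 5-22. The concurrent row with bilirubin at least 2 x ULN has the any-time e-DISH row. The concurrent row with bilirubin at least 1.5 x ULN has neither, so a pair completed on consecutive dates that reaches 1.5 but not 2 x ULN enters no combined-elevation count.

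**The case against.** The strongest reply is that nothing of substance is lost. A split-draw case is counted in both rows of Table 5-22, and the participant's ALT, AST, bilirubin and ALP are listed for all visits. Every post-treatment ALT or AST of at least 3 x ULN goes to adjudication whatever the bilirubin timing. The dedicated Hy's law table already follows the protocol. Discordance also needs unusual circumstances: the analytes share one panel, the protocol's repeat falls outside both windows, and samples go to a central laboratory, so a result-driven redraw within 24 hours is unlikely. Relabelling the Table 6-13 row as same-day would also remove the ambiguity.

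Most of this stands and limits the point. A reader might infer that a Hy's law signal could be missed, or that the hepatic conclusion could change. The documents do not support that, because Table 5-22, the listings and adjudication retain the case. Nor does every case completed the next morning drop out of Table 6-13: pattern C still counts.

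A reader might also see a parallel slip in SAP Table 6-12, which flags ALT and AST only above 3 x ULN. That is not an error. Protocol 7.3.2.3 leaves these criteria to the SAP, the numeric high limits in Table 6-12 all use a strict inequality, and a value of exactly 3 x ULN is captured in Table 6-13 and by adjudication.

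Finally, Protocol 7.3.2.7 sets the 24-hour window for potential Hy's law only. Extending it to the concurrent-elevation rows is a matter of consistency; the protocol does not require it.

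The reply does not remove the mismatch itself: one label, the same limits, two timing rules, and no explanation.

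**Conclusion.** The inconsistency is real, and Table 6-13 is the table out of line with the protocol. Its potential Hy's law count can be lower than that of Table 5-22 for the same arm, by 0.25 percentage points per discordant case at 400 per arm. The expected number of such cases is small, and the documents give no basis for estimating it. The harm is confined to unequal counts under one label and to the 1.5 x ULN concurrent row having only the narrow rule.

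This rests on three readings. Same day is taken as the same calendar date, its ordinary meaning, though the SAP does not use the word calendar. Table 6-13 is taken to be the table meant by the liver function row of Table 5-21, despite the wrong reference there. The arm size is the planned one; the Safety population in the ubrogepant arms is limited to patients who took a dose and may be smaller, which would make one case slightly more than 0.25%.

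**What to change.** In SAP Table 6-13, replace footnote 1 for the potential Hy's law row with the timing used in Table 5-22: "based on blood draws collected within a 24-hour period". Preferably apply the same wording to the two concurrent-elevation rows, so that all combined elevations in the table follow one rule. By Step 2, this can only leave the Table 6-13 potential Hy's law count unchanged or raise it to that of Table 5-22. If a same-day count is wanted for its own sake, label the row as same-day so that it cannot be confused with the protocol-defined count.

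In Table 5-21, change the liver function cross-reference from Table 6-10, Section 6.3.4.2 to Table 6-13, Section 6.3.5.2.

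The cost is one footnote and one cross-reference, with the matching programming specification, before database lock. No data collection, reporting duty or clinical rule changes, and Table 6-12 can stay as it is.
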